8.4.2 Serious Adverse Events (SAEs)

An SAE is defined as any adverse drug experience occurring at any dose that results in any of the following outcomes: death, a life-threatening adverse drug experience, subject hospitalization or prolongation of an existing hospitalization, a persistent or significant disability/incapacity, or a congenital anomaly/birth defect. An important medical event that may not result in death, be life-threatening, or require hospitalization may be considered an SAE when, based upon appropriate medical judgment, it may jeopardize the subject and may require medical or surgical intervention to prevent one of the outcomes listed in this definition.

8.4.3 Clinical Laboratory Parameters

Table 1 shows the laboratory parameters that will be tested in this study. Only parameters tested by the central laboratory will be analyzed. Clinical laboratory data will be transferred from the central laboratory

and converted to International System (SI) units for analysis. Baseline laboratory parameters are those lab parameters collected closest in time, but prior to, randomization.

Table 1: Laboratory Parameters

HEMATOLOGY	CLINICAL CHEMISTRY
Hemoglobin (Hgb)	Total bilirubin
Hematocrit	Alkaline phosphatase
Red blood cell count (RBC)	Lactate Dehydrogenase (LDH)
White blood cell count (WBC)	Alanine aminotransferase (ALT/SGPT)
Absolute neutrophil count (ANC)	Aspartate aminotransferase (AST/SGOT)
Lymphocyte count	Blood urea nitrogen (BUN)
Monocyte count	Serum creatinine
Eosinophil count	Calcium
Basophil count	Magnesium
Platelet count	Glucose
OTHER BLOOD TESTS	Albumin
Total testosterone	Total Protein
Prostate-specific antigen (PSA)	Sodium
VIRAL SEROLOGY	Potassium
Human Immunodeficiency Virus (HIV-1 and HIV-2)	Bicarbonate
Hepatitis panel (HBsAg, HBsAb, HBcAb, HCV antibody (Ab), if Ab+ then HCV RNA))	Chloride
Human T-Lymphotropic Virus (HTLV-1, HTLV-2)	Phosphorus

The following laboratory abnormalities will be considered AEs and recorded in the subject's medical record and on the eCRF:

- Any clinically significant result that is not part of another reported clinical diagnosis
- Any result that meets the definition of an SAE
- Any result leading to discontinuation or interruption of sipuleucel-T
- Any result that requires therapeutic intervention or a change in subject management

Laboratory abnormalities that do not meet the above conditions will not be recorded on the eCRF.

8.4.4 Physical Examination and Vital Signs

Results of physical examinations of body systems (normal/abnormal) are captured on the Physical Examinations CRF at screening. The vital signs collected on this study are height (cm), weight (kg), body temperature (°C), systolic and diastolic blood pressure (mmHg), pulse (beats/min), and respiratory rate (breaths/min). These are entered on the Vital Signs Screening CRFs in the Screening and Leukapheresis folders. Baseline physical exam results and vital signs are the last collected any time prior to randomization.

8.4.5 Electrocardiograms (ECGs)

12-Lead ECGs will be performed at screening and read locally for normality/abnormality. Any abnormalities noted at screening will be included in the Medical History CRF.

8.4.6 Digital Rectal Examinations (DREs)

Findings from DREs (abnormal – yes/no with a description of the abnormality) will be recorded at screening and every 6 months post-randomization on the Digital Rectal Examinations CRFs. Abnormal findings will be reported on the Medical History CRF. Abnormal findings post-randomization will be recorded on the Adverse Events CRF.

9.0 Analysis Sets

9.1 Intention-to-Treat (ITT)

The ITT analysis set is defined as all randomized subjects, regardless of whether any dose of treatment was received. Subjects in this analysis set will be analyzed according to the study treatment assigned at randomization. Subjects who are randomized into the sipuleucel-T arm but are replaced per protocol section 6.4 (as described below), will be included in the ITT analysis set. This analysis set will be used for the primary analyses of the primary endpoint and the secondary efficacy endpoints.

9.1.1 Replaced Subjects

Per protocol section 6.4, subjects who are randomized to the sipuleucel-T arm, but do not receive any sipuleucel-T (>0 mL) may be replaced. Thus, subjects randomized to the sipuleucel-T arm but are found to be ineligible for the study post-randomization or withdraw consent prior to receiving sipuleucel-T therapy are referred to the Medical Monitor. Should the Medical Monitor agree to replacing the subject, he marks the subject eligible for replacement in an Interactive Response Technology (IRT) system. All subjects retain the randomization number assigned. The replacement subject is assigned a new randomization number and linked to the original (replaced) subject in the IRT system.

There are three classifications for subject status in the IRT system: Randomized, Replaceable, and Replaced. A subject having a status of "Randomized" would become "Replaceable" once his replacement eligibility has been changed to "Eligible". Further, a subject having a status of "Replaceable" would become "Replaced" once the subject has been replaced by another subject randomized into the same strata.

The Medical Monitor has the administrative access to change subject's replacement eligibility. When a subject is marked as eligible for replacement within the same strata, the system will assign new subject for replacement with a mirror image randomization number. A randomized subject may be replaced up to 2 times.

9.2 Per Protocol (PP)

The per protocol analysis set is defined as all randomized subjects meeting inclusion and exclusion criteria requirements who have both baseline and month 36 post-randomization ISUP grade group evaluated, who have received the study treatment to which they were randomized, and who were correctly stratified into ISUP grade and number of biopsies groups. If randomized to the sipuleucel-T arm, subjects must have completed all three scheduled infusions. Subjects who are randomized into the sipuleucel-T arm without receiving any sipuleucel-T but get replaced will not be included in the PP analysis set.

Subjects who meet these criteria are considered to be evaluable for the assessment of efficacy per the protocol as planned. Subjects in this analysis set will be analyzed according to the study treatment assigned at randomization. This analysis set will be used for the sensitivity analyses of the primary endpoint and the secondary efficacy endpoints.

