6.7 Restricted Therapies During Sipuleucel-T Treatment Period

Certain therapies and procedures could confound the results of this study. Therefore, subjects who are randomized to the sipuleucel-T arm and receive any of the following, 30 days prior to the first infusion until 30 days after the last infusion, will discontinue sipuleucel-T treatment (Section 6.3.1):

- Any immunosuppressive therapy, including systemic steroids. Use of inhaled, intra-nasal, intra-articular, and topical steroids is allowed. Oral or IV steroids to prevent or treat IV contrast reactions are allowed
- Blood products
- GM-CSF or G-CSF
- Any vaccinations

Subjects that discontinue sipuleucel-T treatment and have received > 0 mL of sipuleucel-T will remain in the Active Phase and follow the schedule of events (Table 1).

6.8 Restricted Therapies from Randomization to End of Active Phase (Sipuleucel-T and Control Arms)

Certain therapies and procedures could confound the results of this study. Therefore, subjects who receive any of the following will go from Active Phase of the study to the Follow-up Phase of the study:

- Any local or systemic therapy or procedures for prostate cancer (e.g., ADT, radical prostatectomy, external beam radiation or brachytherapy)
- Any local or systemic therapy or procedure targeting the prostate (e.g., transurethral resection of the prostate (TURP) or 5-alpha reductase inhibitor)
- Major surgery at the discretion of the sponsor's Medical Monitor
- Any investigational product for prostate cancer or other condition (per sponsor's Medical Monitor approval)
- Any other therapy at the discretion of the sponsor's Medical Monitor

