6.0 Study Design

6.1 Overall Design

This is a multicenter, randomized, open-label study of immunotherapy with sipuleucel-T compared to control subjects followed on AS. The study will enroll subjects being followed by AS and initially diagnosed within 12 months prior to screening with either International Society of Urological Pathology (ISUP) Grade Group 1 or 2 adenocarcinoma of the prostate.

This study consists of 3 phases: the screening phase, the active phase, and the follow-up phase. A schematic of the study can be seen in [Figure 1](#).

Screening Phase:

The Screening Phase will begin at the completion of the informed consent process and continues until randomization. Screening procedures will be performed up to 30 days prior to randomization.

The following assessments will be performed on all subjects during the Screening Phase:

- Blinded Independent Central Review (BICR) of prostate biopsy slides obtained from local pathologists (for ISUP Grade Group and Gleason Score)
- Clinical evaluations (for demographics, medical history, physical examination (PE) & vital signs, digital rectal examination (DRE), Eastern Cooperative Oncology Group (ECOG) performance status, cardiovascular risk assessment & electrocardiogram (ECG))
- Cardiovascular and thrombosis disease history
- Concomitant medications
- All anti-prostate cancer therapies
- Patient-reported outcomes (PROs)/Quality of life questionnaires
- Virology serology (HBsAg, HBsAb, HBcAb, HCV antibody (Ab), if Ab positive (Ab+) then HCV RNA), HIV-1, HIV-2 antibody screen and HTLV-1, HTLV-2 antibodies
- Hematology and chemistry
- Prostate-specific antigen (PSA)
- Total testosterone

Active Phase:

The Active Phase will begin at randomization and continues through completion of the end of Active Phase study visit (within 30 days of Biopsy 2) or until the study is terminated by the Sponsor. If subjects receive the restricted therapies or procedures (Section 6.8 of the protocol), their Active Phase will stop upon receipt of any of these therapies or procedures.

Whenever possible, subjects who discontinue from the study prior to completing the end of Active Phase study visit will undergo an Early Withdrawal visit within 30 days following discontinuation notice. Subjects are encouraged to have, as standard of care, a systematic prostate biopsy (≥ 10 cores) with or without MRI at the Investigator's discretion prior to study withdrawal. The hematoxylin and eosin

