12.6 Efficacy Analyses

12.6.1 Primary Endpoint

The counts and proportions of subjects without ISUP Gleason group upgrade within 36 months of randomization will be presented by study treatment arm and overall. Exact 95% confidence intervals (CIs) for the proportions and the odds of no upgrade will also be presented. The reasons for failure (upgrade within 36 months) will be summarized as well. The exact Cochran-Mantel-Haenszel test of the null hypothesis of no difference in the odds of no ISUP grade group upgrade across treatment arms, while accounting for stratification by baseline ISUP grade group and number of biopsies, will be performed in the ITT analysis set.

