12.6.1.1 Methods for Handling Dropouts and Missing Data

Missing baseline or post-baseline ISUP grade group will result in imputed failure status as defined in [Section 8.1.1](#). These methods allow for a conservative estimate of the proportion that do not have ISUP grade group upgrade if information is not available to determine no upgrade. The pattern of missingness across study treatment arms will be explored using a Kaplan-Meier plot of missing ISUP grade group assessments across time.

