12.6.1.3 Sensitivity Analyses

To evaluate the impact of the potential asymmetric drop-outs, the exact Cochran-Mantel-Haenszel test of the null hypothesis of no difference in the odds of no ISUP grade group upgrade across treatment arms, while accounting for stratification by baseline ISUP grade group and number of biopsies, will be repeated in the per protocol analysis set as a sensitivity analysis.

In a separate sensitivity analysis, the last observation carried forward method will be applied to the primary endpoint in the ITT analysis set. In other words, all subjects with non-missing ISUP grade group at baseline and without any upgrading within 36 months after randomization (even without any post-randomization ISUP grade group) will be counted as successes in the primary efficacy endpoint. Subjects upgrading before 36 months, those with an upgrade at Biopsy 2, or those with missing ISUP grade group at baseline will be counted as failures.

Three sipuleucel-T subjects were replaced pursuant to protocol section 6.4. Sensitivity analyses will be conducted to evaluate the impact, if any, of the inclusion of these subjects in the analysis of the primary and secondary endpoints.

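### The per protocol set is named as the check on asymmetric drop-out, but its month-36-grade condition removes men already known to have upgraded, so the check is sound only under conditions the plan does not state

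*SAP*

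**What the plan says.** - **Primary analysis.** SAP 12.6.1 applies to the ITT set "The exact Cochran-Mantel-Haenszel test of the null hypothesis", stratified by the two randomization factors. Under SAP 8.1.1 an upgrade before 36 months is a failure, and so is a missing Biopsy 2 grade.
- **Role of PP.** SAP 12.6.1.3 repeats that test in PP, with the stated purpose "To evaluate the impact of the potential asymmetric drop-outs".
- **Entry to PP.** SAP 9.2 admits eligible, correctly stratified men "who have both baseline and month 36 post-randomization ISUP grade group evaluated". It adds: "If randomized to the sipuleucel-T arm, subjects must have completed all three scheduled infusions". Protocol 10.2 defines PP more briefly, as men who completed all assessments.
- **Effect of treatment on follow-up.** Protocol 6.8 states that "subjects who receive any of the following will go from Active Phase of the study to the Follow-up Phase of the study", and prostate cancer therapy is on the list. SAP 6.1 says that "their Active Phase will stop upon receipt of any of these therapies or procedures". The Follow-up Phase assessments include no biopsy. Under protocol 8.11, an upgraded man who stays on surveillance continues the Active Phase schedule.
- **Substitute grades.** SAP 8.1.1 lets a centrally read grade within 90 days of the 36-month visit stand in for a missing Biopsy 2.
- **Other checks.** A carry-forward analysis in ITT takes men with a baseline grade and no recorded upgrade: "even without any post-randomization ISUP grade group) will be counted as successes". Missingness by arm "will be explored using a Kaplan-Meier plot of missing ISUP grade group assessments across time" (SAP 12.6.1.1).
- **Subsequent treatment.** SAP 12.6.2.1 reports the proportion treated and the time to first treatment in both ITT and PP. Protocol 10.3 asks for all efficacy analyses in both sets.

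**The concern.** A drop-out check should show how the result depends on men whose final biopsy is missing. PP removes all of those men. It also removes some whose outcome is known: those upgraded at Biopsy 1 and treated before Biopsy 2. This is not a remote case, because protocol 2.1.1 presents grade upgrading as a reason to switch to active treatment. The trial is open-label, so uptake of treatment after an upgrade could differ by arm.

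Two outputs are at stake. One is the PP odds ratio, which a reader would take as reassurance, or as a warning, about drop-out. The other is the PP treatment summary, which leaves out nearly all men treated before the Biopsy 2 window opens.

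**Working it through.** **The plan's own figures.** Success of 0.84 vs 0.70 gives (0.84/0.16)/(0.70/0.30) = 5.25/2.333 = 2.25, as stated. With 300 vs 150 men and one-sided 0.025, unstratified exact (Fisher) power is 0.9025, matching the stated 90%.

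**Inputs.** From the documents: 0.84, 0.70, 300:150, one-sided 0.025. The documents give no timing of upgrades, treatment uptake or loss of Biopsy 2, so all of these are assumed. Let e and l be the proportions upgraded at Biopsy 1 and at Biopsy 2, and s = 1 − e − l. Let t be the share of early upgraders treated before Biopsy 2. Let g be the loss of Biopsy 2 among men not upgraded at Biopsy 1, and h that loss among untreated early upgraders. Half of upgrades are assumed early: e = l = 0.08 (sipuleucel-T, design), 0.15 (control), and 0.15 in both arms under no effect. Pairs below are sipuleucel-T vs control.

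PP success = s(1−g) / [s(1−g) + l(1−g) + e(1−t)(1−h)]

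**1. Equal uptake (t = 0.7), no other loss.** 0.84/(0.84+0.08+0.024) = 0.84/0.944 = 0.890, and 0.70/(0.70+0.15+0.045) = 0.70/0.895 = 0.782. OR = (0.84/0.104)/(0.70/0.195) = 2.25. Both proportions are overstated; the odds ratio is not biased.

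**2. Unequal uptake, no other loss.** PP OR = true OR × (1−r_c)/(1−r_s), where r = e·t/(e+l) = t/2 is the share of an arm's upgraders removed.
- 70% vs 50%, no effect: 0.75/0.65 = 1.15. One-sided rejection is about 0.067 by unstratified Fisher simulation, against about 0.020 without selection. The plan's test is exact and stratified, so this is a stand-in.
- 70% vs 50%, design effect: 2.25 × 0.75/0.65 = 2.60.
- 50% vs 70%, design effect: 2.25 × 0.65/0.75 = 1.95.
- 70% vs 60%, no effect: 0.70/0.65 = 1.08.
- If 60% of upgrades are early and uptake is 30% in one arm and 70% in the other, r is 0.18 and 0.42, and the no-effect OR is 0.58/0.82 = 0.71 or 0.82/0.58 = 1.41.

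**3. Unequal loss of Biopsy 2 (10% vs 30%), no effect.** If h = g in each arm, (1−g) cancels. PP then gives OR 1.00 with equal uptake and 1.15 with uptake 70% vs 50%, the same as without loss. If instead untreated early upgraders never miss Biopsy 2 (h = 0), equal uptake of 70% gives (0.63/0.18)/(0.49/0.15) = 1.07. Nothing in the documents supports that last assumption.

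**4. The two ITT analyses, no effect.** Primary scoring is s(1−g); carry-forward is 1 − e − l(1−g).

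| Loss | Primary | OR | Carry-forward | OR |
|---|---|---|---|---|
| 10% vs 20% | 0.63 vs 0.56 | 1.34 | 0.715 vs 0.730 | 0.93 |
| 10% vs 30% | 0.63 vs 0.49 | 1.77 | 0.715 vs 0.745 | 0.86 |

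**5. Three-infusion condition, no effect.** If a fraction f do not complete and their success is 0.15 lower, completers' success is 0.70 + 0.15f. For f = 0.05 this is 0.7075 (OR 1.04); for f = 0.15 it is 0.7225 (OR 1.12).

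**6. Proportion treated (uptake q after Biopsy 2).** ITT: e·t + l·q. PP: l·q/(1 − e·t). With t = q = 0.7: ITT 11.2% vs 21.0%, PP 0.056/0.944 = 5.9% vs 0.105/0.895 = 11.7%. With q = 0.35: ITT 8.4% vs 15.8%, PP 3.0% vs 5.9%. On the SAP's 30-day month, the 36-month window opens at day 36×30 − 90 = 990, about week 141. The PP time-to-treatment curve is nearly flat until then by construction.

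**7. Candidate repairs, no effect, loss 10% vs 30%.** PP edited to keep every early upgrader as a failure, s(1−g)/[s(1−g)+l(1−g)+e]: 0.63/0.915 = 0.689 vs 0.49/0.745 = 0.658, OR 1.15. ITT imputation at each arm's observed late-upgrade risk: OR 1.00 if loss is unrelated to outcome. If lost men have k times the late-upgrade risk of observed men, the observed risk is (0.15/0.85)/(1+(k−1)g). Then k = 2 gives success 0.714 vs 0.735 (OR 0.90), and k = 0.5 gives 0.692 vs 0.674 (OR 1.09).

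**The case against.** The strongest case is that PP can work. If untreated early upgraders miss Biopsy 2 at the same rate as other men, uptake is equal by arm and loss is unrelated to outcome, PP gives OR 1.00 at 10% vs 30% loss, while primary scoring gives 1.77. This stands. A reader might infer from SAP 9.2 that PP can never serve as a drop-out check; the definition does not support that.

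A reader might also take the one-arm infusion rule for an error. It is ordinary per protocol practice, since control men have no infusions to complete. It limits interpretation if non-completion is related to outcome, and no more.

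The other safeguards are real. Success rests on one ITT test (SAP 12.6.1.2). The carry-forward analysis keeps every observed upgrade as a failure. In the cases run, the two ITT analyses bracket the true odds ratio, so a divergence would be visible. Treatment is also reported in ITT, so no information is lost there. But the two ITT results can fall far apart on either side of 1, the missingness plot is descriptive, and PP is the only planned analysis of the primary endpoint that scores the missing results neither all as failures nor all as successes.

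**Conclusion.** The point holds in limited form. From the text alone, PP drops confirmed failures who are treated before Biopsy 2, unless a centrally read grade falls within 90 days of month 36. Its success proportions are overstated when early upgraders are lost more often than other men.

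The PP odds ratio can be relied on only if uptake and upgrade timing among early upgraders are equal by arm, and if loss of Biopsy 2 and non-completion of infusions are unrelated to outcome. The plan states none of these conditions. Under the assumed 20-point uptake difference the odds ratio shifts by a factor of about 1.15 in either direction, so a bias specifically in favour of sipuleucel-T is not shown. The sizes are illustrations; the mechanism does not depend on them.

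It would be wrong to infer that the primary result is compromised: the primary ITT test and the success criterion are untouched, and the PP treatment output is descriptive. The change should be made before results are known, but it is not critical to the trial's validity.

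**What to change.** 1. **SAP 12.6.1.3 (the main change).** Label PP a supportive analysis of compliant completers. Make the drop-out check an ITT analysis that keeps every centrally confirmed upgrade as a failure and multiply imputes missing Biopsy 2 results for non-upgraded men, within arm and by the two randomization factors. Add a tipping-point shift in late-upgrade risk that varies separately by arm; step 7 of the working shows why imputation alone is not enough. Keep as failures, or otherwise pre-specify, non-upgraded men treated before Biopsy 2 and men who end participation for locally advanced or metastatic disease (protocol 6.3.2).
2. **SAP 12.6.2.1.** Base conclusions on subsequent treatment on ITT. Protocol 10.3 also requires a PP version: drop the month-36-grade condition for it, or record a departure from the protocol.
3. **Optional, SAP 9.2.** Count an earlier centrally confirmed upgrade as an evaluable PP failure, and align protocol 10.2. This removes the bias from unequal uptake. The odds ratio is still biased if loss of Biopsy 2 differs by arm (1.15 at 10% vs 30% under no effect), so it does not replace change 1.

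Cost: SAP text edits, a protocol alignment or recorded departure where needed, and one more programmed ITT analysis. No new data are required.

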9.3 Safety

The safety analysis set is defined as all randomized subjects who have had any dose of study treatment, i.e., all subjects randomized to the control arm and all subjects randomized to the sipuleucel-T arm who have had some part of their first infusion. Subjects who are randomized into the sipuleucel-T arm, but are replaced per protocol section 6.4, will not be included in the safety analysis set. Subjects in this analysis set will be analyzed according to the study treatment actually received. This analysis set will be used for analysis of the safety endpoints and variables.

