6.3.1 Discontinuation from Sipuleucel-T Arm

Declining the first sipuleucel-T infusion or associated leukapheresis will result in an automatic withdrawal from the study. Subjects will complete an early withdraw visit within 30 days of the scheduled sipuleucel-T infusion.

Sipuleucel-T will be discontinued if a subject meets any of the following criteria:

- The subject never undergoes a leukapheresis for the purpose of receiving sipuleucel-T
- The subject undergoes leukapheresis, but is unable to receive at least 1 partial (>0 mL) sipuleucel-T infusion for any reason at the discretion of sponsor's Medical Monitor
- Inability to manufacture sipuleucel-T in the opinion of the sponsor's medical monitor
- The subject experiences intolerable toxicity
- Significant infection at the discretion of sponsor's Medical Monitor

- CVE or TIA of any grade prior to completion of 3 sipuleucel-T infusions
- Withdrawal of consent for continued sipuleucel-T infusions
- The subject fails to comply with protocol-specified procedures or protocol requirements
- Sponsor terminates the study
- The subject is discontinued from the study at the discretion of the investigator or sponsor

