6.4 Replacement of Subjects

Subjects who are randomized to the sipuleucel-T arm, but do not receive any sipuleucel-T (>0 mL) may be replaced.

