7.2 Sipuleucel-T Treatment

7.2.1 Leukapheresis and Infusion Scheduling

Once a subject has completed screening assessments and has been confirmed to be eligible and randomized to the sipuleucel-T arm, Dendreon will designate a leukapheresis center and the site will request a schedule for the subject's leukapheresis procedures to occur at approximately 2-week intervals. The date of each leukapheresis procedure will determine the date for the subsequent infusion of sipuleucel-T (approximately 3 days later).

The clinical trial site will receive confirmation of the leukapheresis and infusion dates and will schedule the subject's infusion appointments accordingly. If the subject is subsequently deemed ineligible for the study, the clinical trial site will be informed and the leukapheresis and infusion appointments will be canceled.

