10.2 Analysis Populations

The Safety Analysis Population is defined as all randomized patients; the Sipuleucel-T safety population must have begun the treatment process.

The intent-to-treat (ITT) population is defined as all randomized subjects.

The Per Protocol (PP) population is defined as the subset of patients in the ITT population who have completed all assessment per the protocol.

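### SAP 9.3 admits sipuleucel-T men to the safety set only at infusion, so men leukapheresed but never infused miss the aggregate AE and SAE tables that SAP 8.4.1 opens at leukapheresis; AE counting also starts later in that arm than in control

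*SAP*

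**What the plan says.** **Who is in the set.** SAP 9.3 takes all control men and, in the other arm, "all subjects randomized to the sipuleucel-T arm who have had some part of their first infusion". Men who "are replaced per protocol section 6.4, will not be included in the safety analysis set". The set serves the safety endpoints and variables, and "Subjects in this analysis set will be analyzed according to the study treatment actually received". Protocol 10.2 starts from all randomized men and adds that "the Sipuleucel-T safety population must have begun the treatment process". It does not say when that process begins.

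**Which events are counted.** AEs and SAEs are collected from randomization in both arms (protocol 9.1.4, SAP 8.4.1). SAP 8.4.1 then summarizes them from first leukapheresis in the sipuleucel-T arm and from randomization in control. First leukapheresis may fall up to 60 days after randomization (SAP 6.1).

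**Where they are shown.** SAP 12.7.1 puts the AE, grade 3 or higher, SAE, related-AE and fatal-AE tables in the Safety population. It also plans a table of AEs within 1 day after any leukapheresis. SAP 12.7.2 sends SAE analyses back to 12.7.1. SAP 12.4.1 counts leukaphereses and central venous catheter use in the ITT set.

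**The case is foreseen.** Protocol 6.3.1 lists as a reason for stopping sipuleucel-T: "The subject undergoes leukapheresis, but is unable to receive at least 1 partial (>0 mL) sipuleucel-T infusion for any reason".

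**The concern.** Leukapheresis is a required step of the treatment under test, and the SAP recognizes this by opening the AE window there and planning a table for it. The population rule then removes the men whose only exposure was that step. A man stopped by a leukapheresis complication before infusion 1 would be in the exposure count but not in the table meant to show such complications.

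A second issue is independent of how many such men there are. Events between randomization and first leukapheresis are collected in both arms but summarized only in control, so the two arms' AE percentages cover different periods.

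**Working it through.** The plan gives no figure on this point to reproduce. The definitions are compared first, and then the possible size is bounded with stated assumptions.

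**1. A man leukapheresed but never infused, followed through the plan**

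| Output | Population or start | Is he counted? |
|---|---|---|
| Leukapheresis and catheter exposure (SAP 12.4.1) | ITT, sipuleucel-T arm | Yes |
| AE window (SAP 8.4.1) | From first leukapheresis | His events fall inside it |
| AE and SAE tables, including post-leukapheresis (SAP 12.7.1) | Safety set, from infusion 1 | No |
| Deaths from all causes (SAP 12.7.2) | All randomized | Yes |
| Disposition and reasons for stopping (SAP 12.2) | Not limited to the safety set | Yes |
| AE listings (SAP 12.7.1) | Not stated | Unclear |

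SAE reporting to the sponsor, safety review by the data monitoring committee, and the leukapheresis events of men who were later infused are also unaffected.

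**2. Effect of leaving out never-infused men**

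Let k be the number of such men and h the number of them with a given harm. Neither is in the documents. Assume an arm of 300 (the planned size), all leukapheresed, with 3 infused men having an uncommon harm and k = 3.

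- Reported under SAP 9.3: 3/(300 − 3) = 3/297 = 1.01%.
- With the excluded men: (3 + h)/300 = 1.00%, 1.33%, 1.67% or 2.00% for h = 0, 1, 2 or 3. The last is the extreme case.
- With k = 1: reported 3/299 = 1.00%; full rate 3/300 = 1.00% or 4/300 = 1.33%.
- Common AE, assumed in 240 of 300 (80.0%), k = 3: reported 237/297 = 79.8% if all three had it, or 240/297 = 80.8% if none did.

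Common events barely move, and the error can go either way. With k = 0 nothing changes.

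**3. Effect of the unequal start**

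Assume equal constant hazards in the two arms and the same wait for every sipuleucel-T man. Let p be the incidence from randomization and f the share of follow-up not summarized:

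- f = wait in days / (months × 30.4375); shown incidence = 1 − (1 − p)^(1 − f).
- The loss is largest where 1 − p = q = (1 − f)^(1/f), and there it equals q × f/(1 − f).
- 36 months, 60-day wait: f = 60/1095.75 = 0.0548; q = 0.3575; largest loss = 0.3575 × 0.0548/0.9452 = 0.0207, or about 2.1 points, at p of about 0.64.
- 36 months, 30-day wait: f = 0.0274; largest loss about 1.0 point.
- An event with p = 5% over 36 months and a 60-day wait is shown as 1 − 0.95^0.9452 = 4.73%.

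The same formula gives up to 6.6 points at 12 months and 3.15 at 24 months with a 60-day wait. Those figures describe men who leave early, since planned follow-up is at least 36 months.

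**The case against.** **Two rules can coexist.** SAP 8.4.1 sets a time window and SAP 9.3 a population. Applied together, they count every infused man's events from his first leukapheresis. That is coherent for infused men, and it stands. It does not help the post-leukapheresis table, which still loses never-infused men, or square with the SAP 8.4.1 statement that all events after first leukapheresis are summarized.

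**The protocol may itself mean infusion.** A reader might infer that the SAP plainly contradicts protocol 10.2. The documents do not support that. The placement of leukapheresis within protocol 7.2 is weak evidence, because that section opens with "7.2.1 Leukapheresis and Infusion Scheduling" and the procedure itself comes only in 7.2.4. Other text points to infusion. Replacement concerns men who are randomized "but do not receive any sipuleucel-T (>0 mL) may be replaced", and men who stop treatment but "have received > 0 mL of sipuleucel-T will remain in the Active Phase". Relatedness is judged from administration of the product (protocol 9.1.3), and the protocol's own timed AE table is tied to infusion (10.5.5.1). The phrase is undefined, so the SAP only appears narrower.

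**The number may be nil.** A reader might take the three replaced men (SAP 12.6.1.3) as the missing cases. Nothing says they were leukapheresed, and SAP 9.1.1 describes replacement for ineligibility or withdrawn consent. Repeat leukapheresis is allowed (protocol 7.2.6), which also keeps k down. On the other hand, replacement is optional, so three is not an upper limit.

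**Much is already visible.** SAP 12.4.1 lets k be read by subtraction (men with at least one leukapheresis minus men with at least one infusion), and SAP 12.2 shows reasons for stopping. This stands, and it narrows the gap to coded events in the aggregate tables.

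**Date imputation.** SAP 12.7.5 imputes partial AE start dates from the first dose date, which an uninfused man lacks. Control men lack one too, so this adds little cost.

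**Conclusion.** The point holds in a limited form and should be corrected. As written, the SAP omits men leukapheresed but never infused from the AE and SAE tables, including the one designed around leukapheresis, while counting them as exposed. The effect depends on k, which is not stated and may be zero. If it is a handful, only an uncommon procedure harm could be materially misreported: under the assumed inputs, 1.01% against at most 2.00%.

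The unequal start applies to the whole sipuleucel-T arm but is modest: at most about 2.1 points on any-AE incidence over 36 months, and about 1.0 point with a 30-day wait. Both bounds assume equal constant hazards and a uniform wait. Losses are larger only for men who leave early.

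A reader might infer that the plan hides toxicity in the sipuleucel-T arm. The documents do not support that. Leaving men out can raise or lower a rate, the later start lowers it under the assumptions above, and the net direction is not established.

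**What to change.** (a) Reconcile SAP 9.3 with protocol 10.2 and SAP 8.4.1, with the sponsor confirming what the protocol's entry condition means. At minimum, run the post-leukapheresis AE table in all men who began a first leukapheresis, whether or not they were infused or replaced. State that they count in the sipuleucel-T arm, because analysis by treatment received is unclear for a man never infused. Keep the post-infusion table for infused men.

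(b) Add a supplementary between-arm AE and SAE table, counted from randomization in all randomized men in both arms. A leukapheresis-based set alone would still drop earlier events in one arm only.

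Cost: minor edits to the SAP and table shells; the events are already collected from randomization in both arms. The downside is that a few men with short follow-up enter the denominator (declining the first infusion means withdrawal from the study, protocol 6.3.1), and some background events before leukapheresis are counted.
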